### 7.8.3 Additional Efficacy Endpoint(s)

Not applicable

## 7.9 Pharmacokinetic/Pharmacodynamic Analysis

### 7.9.1 Pharmacokinetic Analysis

Serum concentrations of brentuximab vedotin (ADC) and total therapeutic antibody (TAb), and plasma concentrations of monomethyl auristatin E (MMAE) will be determined using validated assays.

Descriptive statistics (eg, number of patients, arithmetic mean, geometric mean, StdDev, median, percentage of coefficient of variation (%CV), minimum, and maximum) will be used to summarize serum ADC, serum TAb, and plasma MMAE concentrations at each time point in Cycles 1 and 8 at each dose level. The mean concentrations-time profiles of ADC, TAb, and MMAE will be plotted for cycles 1 and 8. The complete set of the same data (Cycles 1-16 or up to the cycle where  $N \geq 3$ ) will also be plotted for each dose level for ADC on a single plot. Similar plots will be provided for the TAb and the MMAE. Individual patient concentration data will be listed and plotted over time by cycle and by dose level.

Noncompartmental analysis for the determination of PK parameters such as  $t_{max}$ ,  $C_{max}$ ,  $AUC_{0-21}$  day,  $AUC_{0-\infty}$ ,  $t_{1/2}$ , CL, and  $V_{ss}$  will be performed as data permits for ADC and TAb. The PK parameters of  $t_{max}$ ,  $C_{max}$ ,  $AUC_{0-21}$  day,  $AUC_{0-\infty}$ , and  $t_{1/2}$  will be estimated for MMAE. These parameters will be summarized by dose level and cycle. The summary statistics will consist of N, mean, StdDev, %CV, median, min, max, and geometric mean.  $AUC_{0-21}$  day or  $AUC_{0-\infty}$  of ADC at 1.4 mg/kg will be scaled to 1.8 mg/kg (parameter to be scaled with multiplication of 1.29) for purposes of evaluating estimated exposures at the 1.8 mg/kg dose across the PK population. The individual CL of ADC and TAb will also be computed by normalizing for the baseline body weight and body surface area. Individual patient values of the parameters will be listed by cycle.

The 1.8 mg/kg and scaled 1.8 mg/kg  $AUC_{0-21}$  day or  $AUC_{0-\infty}$  of ADC will be plotted against age and/or body weight. More exploratory plots may be presented in the CSR as needed.

### 7.9.2 Pharmacodynamic Analysis

Not applicable

## 7.10 Other Outcomes

### 7.10.1 CCI

CCI

### 7.10.2 Immunogenicity Analysis

Immunogenicity will be summarized using descriptive statistics into the following categories: ATA negative, transiently ATA positive, persistently ATA positive, low and high ATA titer, and neutralizing ATA (nATA).

- ATA Negative - defined as patients who do not have positive ATA in any postbaseline sample
- Transiently ATA positive - defined as patients who have positive ATA in 1 or 2 postbaseline samples
- Persistently ATA positive - defined as patients who have positive ATA in more than 2 postbaseline samples
- High ATA Titer:  $>25$
- Low ATA titer:  $\leq 25$
- nATA negative: defined as patients who do not have positive nATA in any postbaseline ATA positive sample
- nATA positive: defined as patients who have positive nATA in any postbaseline ATA positive sample.

ATA status, ATA titer and neutralizing ATA will be listed by patient. Neutralizing ATA status (nATA negative and positive) will also be listed for patients who have positive antibody status.

For effect of ATA on efficacy, the proportion of patients in CR and PR will be summarized within each ATA response status (negative, transiently positive, persistently positive) by disease type. The same analysis may be repeated based on ATA titer (high,  $>25$ ; low,  $\leq 25$ ). In addition, patient level ATA and efficacy (overall response) data will be listed together by time.

For effect of ATA on safety, patient incidence of AEs (preferred term) by ATA response status (negative, transiently positive, persistently positive, high and low titer) will be provided for both HL and sALCL. Infusion-related reactions (preferred term) will also be summarized by ATA status, ATA titer and nATA status.

The relationship between immunogenicity status (ATA, ATA titer, nATA) and PK may be explored.

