### 4.2 Secondary Objectives

Phase 1 secondary objectives are:

- To determine the immunogenicity of brentuximab vedotin
- To determine the best overall response rate (CR, PR) with brentuximab vedotin
- To determine the time to progression, time to response, duration of response, and event-free, progression-free, and overall survival with brentuximab vedotin

Phase 2 secondary objectives are:

- To determine the time to progression, time to response, duration of response, and event-free, progression-free, and overall survival with brentuximab vedotin
- To assess the PK and safety profile of brentuximab vedotin
- To determine the immunogenicity of brentuximab vedotin

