## 7.0 METHODS OF ANALYSIS AND PRESENTATION

### 7.1 General Principles

In general, descriptive statistics (number of observations, mean, standard deviation (StdDev), median, minimum, and maximum) will be used to summarize continuous variables. Frequencies and percentages will be used to summarize categorical variables. Time-to-event data will be analyzed using the Kaplan-Meier method and results will be summarized by the 25th, 50th (median), and 75th percentiles, if estimable, with associated 2-sided 95% confidence intervals, as well as the percentage of censored observations.

Unless otherwise specified, safety and efficacy data will be summarized in the following 7 groups: 1.4 mg/kg phase 1 only; 1.8 mg/kg phase 1 only; 1.8 mg/kg phase 1&2 HL only; 1.8 mg/kg phase 1&2 sALCL only; 1.8 mg/kg phase 1&2 sALCL in first relapse only; 1.8 mg/kg all patients; all patients. Pharmacokinetic analyses will be summarized by dose and treatment cycle.

The baseline value is defined as the value collected at the time closest to, but prior to, the start of study drug administration, unless otherwise specified. A windowing convention will be used to determine the analysis value for a given study visit for observed data analyses.

All available efficacy and safety data will be included in data listings and tabulations. Data that are potentially spurious or erroneous will be examined under the auspices of standard data management operating procedures. In general, there will be no imputation of missing data. For time-related endpoints, subjects who have no specified events will be censored as specified for each respective endpoint in Section 7.8. Imputation rules for missing dates of AEs and concomitant medications are detailed in Sections 7.1.3 and 7.1.4.

SAS Version 9.2 (or higher) will be used for all analyses.

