### **7.2 Analysis Sets**

#### **7.2.1 Safety Population**

The safety population will include patients who have received at least 1 dose of study drug. Safety population will be used for all safety, efficacy, and immunogenicity analyses, unless otherwise specified.

[figure not shown]

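### ATA and nATA status is classified from postbaseline samples only, so the immunogenicity summary cannot separate antibody present before the first dose from antibody induced by the drug

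*SAP*

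**What the plan says.** Section 4.2 makes immunogenicity a secondary objective in both phases: "To determine the immunogenicity of brentuximab vedotin". Section 7.10.2 sets the classes by counting positive results after baseline:

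- The lowest class needs a clean record after dosing: "ATA Negative - defined as patients who do not have positive ATA in any postbaseline sample".
- The middle class is reached with one or two positive results, whatever the predose finding was.
- The top class starts at three: "Persistently ATA positive - defined as patients who have positive ATA in more than 2 postbaseline samples".
- Neutralizing antibody follows the same pattern: "nATA positive: defined as patients who have positive nATA in any postbaseline ATA positive sample".

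Titer is divided at an absolute value of 25, without reference to a baseline titer. The analysis set is not restricted by baseline status; Section 7.2.1 says "Safety population will be used for all safety, efficacy, and immunogenicity analyses, unless otherwise specified". The classes are then carried into further tables: "For effect of ATA on efficacy, the proportion of patients in CR and PR will be summarized within each ATA response status", and likewise AE incidence and infusion-related reactions. Section 7.1 does hold a general baseline definition, "The baseline value is defined as the value collected at the time closest to, but prior to, the start of study drug administration", but Section 7.10.2 does not use it to classify patients.

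**The concern.** The objective asks what antibody the drug provokes. Antibody already present before exposure is not an answer to that, yet under these rules it can be reported as one. Section 7.10.2 itself calls the classes a response status, which invites the reader to take every positive patient as a responder to the drug.

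Elsewhere the SAP does relate safety outcomes to the start of treatment. AEs must begin after the first dose to count as treatment-emergent (Section 7.11.1), and laboratory shift tables run from baseline grade to worst postbaseline grade (Section 7.11.2). The ATA classes have no such anchor.

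At stake is the interpretability of a descriptive secondary result in small disease groups, where one patient is a visible share of the total. The tables of response, AEs and infusion-related reactions by ATA status use the same classes and so give no sign of which positive patients were positive before dosing.

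**Working it through.** The SAP states no figure for immunogenicity that could be reproduced. The check has two parts: apply the rule as written, then show the possible size under labelled assumptions.

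**1. The rule applied to each combination** (Section 7.10.2)

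| Positive postbaseline samples | Baseline negative | Baseline positive |
|---|---|---|
| 0 | ATA negative | ATA negative |
| 1 or 2 | transiently positive | transiently positive |
| 3 or more | persistently positive | persistently positive |

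The two columns are identical, so baseline status has no influence on the class. A patient positive at baseline with three or more unchanged positive samples falls in the same cell as one who seroconverted on treatment. A patient positive at baseline with none afterwards falls in the negative row, and the pre-existing antibody disappears from the summary. The nATA rule has the same structure.

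**2. Ceiling per patient**

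Section 6.0 plans at least 15 evaluable patients per disease. With a denominator of exactly 15, one baseline-positive patient who stays positive without any change adds 1/15 = 6.7 percentage points, and three add 3/15 = 20 points. This is an upper bound. Immunogenicity is analysed in the safety population, so the group may be larger than 15.

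**3. Comparison with the rate among baseline-negative patients**

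Let b be the share positive at baseline, r the share of those with a positive postbaseline sample, and p the induced rate among baseline-negative patients. All three are assumptions; the SAP gives none of them.

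- Rate under the SAP rule = b·r + (1 − b)·p
- Difference from p = b·(r − p)

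With n = 15, r = 1 and p = 20%, the difference is (k/15) × 0.80 for k baseline-positive patients:

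- k = 0: 0 points
- k = 1: 5.3 points
- k = 2: 10.7 points
- k = 3: 16.0 points (36% against 20%)

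With k = 3 and p = 50%, the SAP rate is 0.20 + 0.80 × 0.50 = 60% against 50%, a difference of 10 points.

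**4. By assumed baseline prevalence, p = 20%**

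| b | SAP rate, r = 1 | SAP rate, r = 0.5 | Share of positives that are pre-existing, r = 1 |
|---|---|---|---|
| 0% | 20% | 20% | 0% |
| 5% | 24% | 21.5% | 21% |
| 10% | 28% | 23.0% | 36% |
| 15% | 32% | 24.5% | 47% |

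The last column is b·r divided by the SAP rate; for b = 10%, 0.10/0.28 = 36%. In the planned total of about 42 patients, 5%, 10% and 15% correspond to about 2.1, 4.2 and 6.3 patients.

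The excess over 20% is therefore 4 to 12 points if all baseline-positive patients stay positive, and 1.5 to 4.5 points if half do.

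**The case against.** The categories are clear, reproducible and not contradictory. Immunogenicity is descriptive: no test or decision rule depends on it, no interim analysis is planned (Section 7.12), and the primary endpoint is ORR (Section 7.8.1). By-patient listings of ATA status, titer and nATA are planned, and ATA is also listed together with response over time. With about 42 patients, a baseline-positive patient could be found there if baseline results are listed. The SAP does not suggest that any such patient exists. All of this limits the harm, but a listing does not correct the summary tables.

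Three stronger readings are tempting, and the document does not support them.

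- A reader might infer that every patient positive before dosing is counted as a response, and usually as a persistent one. At least one positive postbaseline sample is needed, and the SAP gives no persistence rate for pre-existing antibody.
- A reader might infer that incidence is overstated by 7 to 20 points. That is the ceiling for one to three patients in a group of exactly 15. It assumes that each stays positive with no rise in titer, since a boosted titer can fairly be counted as a response to the drug. It also leaves out the possibility that no patient is baseline positive.
- A reader might infer that the response, AE and infusion-reaction tables are wrong unless they use treatment-emergent status only. Those tables ask about the effect of ATA, and antibody present while on the drug is a defensible exposure whatever its origin. Moving baseline-positive patients without a titer rise into the negative group, or dropping them, could blur the comparison more than the present rule does.

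**Conclusion.** The point holds as a gap in the classification rule. Followed exactly, Section 7.10.2 reports an unchanged pre-existing antibody as a positive ATA response if it is detected again after dosing, and hides it if it is not. Nothing else visible in the SAP corrects this.

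The size cannot be fixed from the SAP. It is nil with no baseline-positive patients and at most 6.7 points for each one in a group of 15. It is smaller if the patient does not stay positive, if titer rises, if the group is larger, or if the reference is the rate among baseline-negative patients. On that last reference it is about 5 to 16 points for one to three patients who all stay positive, at an assumed 20% induced rate.

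The conclusion assumes that a predose ATA sample is taken, which the word postbaseline implies but the SAP does not state outright. The association tables lack a distinction but are not invalid, and the primary ORR is unaffected. The rule should be settled before baseline ATA results are known.

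**What to change.** In Section 7.10.2:

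1. Tabulate baseline ATA status.
2. Apply the negative, transient and persistent categories to baseline-negative patients, and report their positives as treatment-emergent ATA incidence.
3. Show baseline-positive patients in a separate row, split by whether titer rose after dosing by a margin that the sponsor sets in advance from the assay.
4. In the tables of CR/PR, AEs and infusion-related reactions, keep the on-drug ATA categories but show baseline-positive patients as their own row. Do not merge them into the negative group or drop them.

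If no predose ATA sample is taken, say so, and state that pre-existing and induced antibody cannot be separated.

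The cost is a few lines of SAP text, one derived flag from the baseline sample, and one small extra row per table. If baseline samples are taken as implied, no new sampling is needed, and the trial design does not change.

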### 7.11.1 Adverse Events

AEs will be tabulated according to the Medical Dictionary for Regulatory Activities (MedDRA) Version 19.0 by system organ class, high-level terms, preferred terms and intensity. AEs with missing start and/or end dates will be imputed according rules specified in Section 7.1.3.

Treatment emergent AE is defined as any AE that occurs after administration of the first dose of study treatment and up through 30 days after the last dose of study drug. Patients with the same AE more than once will have that event counted only once within each body system, once within each high-level term, and once within each preferred term. AEs will be summarized and will include the following categories:

- Treatment-emergent AEs
- Drug-related treatment-emergent AEs
- Grade 3 or higher treatment-emergent AEs
- Grade 3 or higher drug-related treatment-emergent AEs
- Treatment-emergent AEs resulting in study drug discontinuation
- SAEs
- AEs of peripheral neuropathy identified by the broad search MedDRA SMQ "Peripheral neuropathy"

Treatment-emergent AEs will be tabulated by system organ class, high-level term and preferred term. The most commonly reported treatment-emergent AEs (i.e., those events reported by  $\geq$  10% of all patients) will be tabulated by preferred term. The individual patient's information on the DLTs will be presented in a listing. Additional analyses of peripheral neuropathy may also be presented.

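### The tables of AEs by ATA status ignore whether the event began before the first positive sample, and they compare patients with unequal time on treatment

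*SAP*

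**What the plan says.** All of the relevant text is in SAP sections 7.10.2 and 7.11.1.

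- **Status (7.10.2).** ATA negative is "defined as patients who do not have positive ATA in any postbaseline sample". Transiently positive is "defined as patients who have positive ATA in 1 or 2 postbaseline samples". Persistently positive is "defined as patients who have positive ATA in more than 2 postbaseline samples". Neutralizing status likewise looks across all postbaseline ATA-positive samples, and the titer categories are cut-offs with no date attached.
- **Safety tables (7.10.2).** The plan is "For effect of ATA on safety, patient incidence of AEs (preferred term) by ATA response status", with high and low titer also named, for HL and for sALCL. In addition, "Infusion-related reactions (preferred term) will also be summarized by ATA status, ATA titer and nATA status".
- **Response (7.10.2).** Besides the table by status, "patient level ATA and efficacy (overall response) data will be listed together by time". No matching listing is planned for AEs.
- **Event window and counting (7.11.1).** "Treatment emergent AE is defined as any AE that occurs after administration of the first dose of study treatment", and the window runs to 30 days after the last dose. A patient with a repeated event is counted "once within each high-level term, and once within each preferred term".

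No section sets an onset condition, a landmark or a split of person-time at first positivity.

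**The concern.** Status is fixed by looking forward over the whole of treatment, while events are counted from the first dose. Followed as written, the plan puts a reaction at the first infusion in the ATA-positive column even when the first positive sample comes many cycles later.

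There is a second, separate problem. A patient on treatment longer gives more samples, and so has more chance of a positive one, and also has more time to have an AE. The persistent category makes this worse because it needs at least three positive samples. A rise from negative through transient to persistent could therefore look like a graded antibody effect when it only follows time on treatment.

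Immunogenicity is a secondary endpoint in both phases, and the SAP introduces these tables as showing the effect of ATA on safety. With about 42 evaluable patients, one or two reactions in the wrong column can change what a reader concludes. Mixing events from before and after first positivity can also dilute a real later increase.

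**Working it through.** **What the SAP supplies.** It gives no rate for ATA conversion, AEs or discontinuation. Its one numerical design statement (section 6.0) is the exact 95% interval for 10 responses in 15 patients. This reproduces as 38.4% to 88.2% against the stated (38%, 88%), but it plays no part here. The only SAP figure used below is the 16-cycle limit (section 4.4).

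**Check by formula.** Let a patient stay on treatment for C cycles, have probability h per cycle of a first event that does not depend on ATA, and first test positive at the end of cycle k. The share of first events that fall before that sample is

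[1 − (1 − h)^k] / [1 − (1 − h)^C].

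With h = 0.10, k = 4, C = 16: (1 − 0.9^4) / (1 − 0.9^16) = 0.344 / 0.815 = 0.42. With C = 8: 0.344 / 0.570 = 0.60.

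**Null simulation.** 400,000 patients per scenario; all rates are assumed.

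- Time on treatment T = min(geometric(0.12), 16) cycles.
- First AE of a given term in cycle A, geometric(h), with h = 2% or 5%, independent of ATA.
- First positive sample in cycle S = 1 + geometric(s), with s = 3% or 6%.
- Ever-positive if S ≤ T; AE counted if A ≤ T; AE before positivity if A < S.

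| h | s | AE incidence, positive / negative | Ratio | Mean cycles, positive / negative | Share of first AEs in positives before first positive | Incidence in positives, onset on or after first positive |
|---|---|---|---|---|---|---|
| 2% | 3% | 20.1% / 11.7% | 1.7 | 11.18 / 6.48 | 50% | 10.1% |
| 2% | 6% | 19.7% / 10.6% | 1.9 | 10.92 / 5.77 | 46% | 10.5% |
| 5% | 3% | 42.2% / 26.1% | 1.6 | 11.19 / 6.47 | 53% | 19.7% |
| 5% | 6% | 41.1% / 23.7% | 1.7 | 10.95 / 5.77 | 50% | 20.5% |

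**Source of the gap.** First events per cycle at risk are equal in ever-positive and never-positive patients: 0.020 in each at h = 2% and 0.050 in each at h = 5%. The excess in crude incidence is thus due to longer exposure.

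**What a count restricted by onset does.** Compare the last column with the negative patients. At h = 5% it gives 19.7% against 26.1% and 20.5% against 23.7%, so a harmless antibody looks protective. Positive patients lose their early window while negative patients keep all of theirs.

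**What a split of person-time does.** Counting cycles before S as ATA-negative and later cycles as ATA-positive gives 0.020 against 0.020 and 0.050 against 0.050, the true null.

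**Sensitivity.** A wider grid used 5% to 20% per cycle for discontinuation and for conversion, and 5% to 10% for the AE. It gave a spurious excess in every scenario, about 12 to 35 percentage points. The ratio ran from 1.3 (72.9% / 56.6%) to 2.3 (37.9% / 16.3%). Between 38% and 62% of first events in positives fell in or before the cycle of first positivity.

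**The case against.** **The SAP is silent rather than wrong.** It does not expressly say that earlier events count. That is so, but nothing excludes them, and sections 7.10.2 and 7.11.1 read together include them.

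**The antibody might still be responsible.** A reader might infer that events before the first positive sample cannot have been caused by ATA. The SAP does not support that. Sampling is intermittent, the first positive sample is a date of detection and not of onset, and a patient positive at baseline has no antibody-free period. Such events cannot be attributed on these data, which is a weaker statement.

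**The crude gap is not a count of misplaced events.** It is tempting to read the near-doubling as the result of counting events before positivity. The equal rates per cycle at risk show that it comes from unequal exposure. Only the share of about one half bears on event order, and both figures rest on assumed rates.

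**The tables are modest in purpose.** They count patients once per preferred term, not every event, and they carry no test or effect estimate. The secondary endpoint is ATA, titer and neutralizing status, not their association with AEs. This limits the importance of the point but does not remove it.

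**The order can be recovered.** ATA results are listed by patient, and section 7.1 promises that all available safety data will be listed. In a small trial a reader could match the two by hand. That is fair, but no planned output brings them together, whereas one does for response.

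**Conclusion.** The point holds as a modest reporting improvement. As planned, the AE and infusion-reaction tables mix events from before and after ATA was first detected, and they compare groups with unequal time on treatment, so they cannot be read as an effect of ATA on safety.

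That conclusion follows from the text and needs no rates. Its size does need them. Under the main assumed null model, about half of the first events in ever-positive patients precede the first positive sample, and crude incidence is 1.6 to 1.9 times that in negative patients. The direction was the same in every scenario tried, while the amount varied widely.

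The primary endpoint, the sample size and the conduct of the trial are not affected. A reader might also conclude that keeping only events after first positivity would cure the tables. It would not, because that contrast is biased the other way.

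**What to change.** In SAP section 7.10.2:

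1. Add AE and infusion-reaction onset dates to the by-time ATA listing already planned for response. In a trial of this size, this is the most useful single change.
2. For ATA-positive patients, and for the neutralizing and titer groups, show events with onset before the first positive sample separately from those with onset on or after it. Let a patient with the term in both periods appear in both, so that once-per-term counting does not hide a later recurrence.
3. Make any positive-versus-negative comparison with exposure-adjusted rates, with person-time before first positivity counted as ATA-negative. Do not compare post-positivity counts alone with whole-treatment counts.
4. Flag AEs with imputed onset. Table 7.1 sets some incomplete dates to the date of first dose, which would place them before first positivity by rule.
5. State that the first positive sample is a detection date, and present baseline-positive patients separately.

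The cost is SAP wording, a date comparison and person-time sums from dates already recorded, with no new data. The drawback is sparse cells. The simulated share of ever-positive patients was 16% to 29%, which is about 7 to 12 of 42 (0.164 × 42 = 6.9; 0.287 × 42 = 12.1) before any split by disease, titer or period. Where counts are that small, the listing should carry the interpretation.
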